3.2. Blood pressure measurement in the clinic

Determination of systolic (SBP) and diastolic (DBP) blood pressure measured by an automatic sphygmomanometer (Omron HBP 1100[®]), in the right upper limb, with the individual seated, after 10 minutes of rest. Three (3) measurements of systolic and diastolic pressure will be performed, with an interval of 1 minute between them and the average will be calculated later, following the recommendations of the Brazilian Guidelines on Hypertension 2020.³⁵

3.3. Measurement of weight and abdominal circumference in the office

For anthropometric evaluation, weight and height will be measured using a Filizola[®] digital scale, and abdominal circumference will be measured using a standardized measuring tape.

3.4. Ambulatory 24-hour blood pressure monitoring (ABPM)

ABPM allows indirect and intermittent bp recording for 24 hours or more while the patient performs his usual activities in wakefulness and during sleep. The Spacelabs[®] Device will

be used, and the following variables will be obtained: mean systolic, diastolic and pulse blood pressure in the periods of 24 hours, wakefulness and sleep, and considered the normality values according to the Brazilian Guidelines on Hypertension 2020³⁵.

3.5. Blood Pressure Monitoring at Home

Patients in the intervention group will be instructed to perform blood pressure measurement at home with a validated automatic device (Omron) that will be delivered on the day of the consultation after the training period. Patients will be instructed to take measurements as recommended by the recent guidelines³⁵, two measurements in the morning and two measurements at night, Monday to Friday, and will enter the values of the 5 days in the application. These values will be evaluated by the medical and nursing team, which will guide the appropriate conduct based on these measures.

3.6. Measurement of capillary glycemia at home

Patients in the intervention group will be instructed to perform capillary glucose measurement at home with a device that will be delivered on the day of the consultation, after the training period. Patients will be instructed to take measurements in the morning fasting, Monday to Sunday, and will enter the values in the application. These values will be evaluated by the medical and nursing team, which will guide the appropriate conduct based on these measures.

3.7. WHOQOL-BREF2 Quality of Life Questionnaire

The WHOQOL-BREF is a questionnaire that tends to evaluate the overall rate of "quality of life" and "satisfaction" with health. Participants answer questions about various aspects of their life in the present and circulate the number that best represents their feeling. The WHOQOL-BREF contains two types of questions: a "positive" where a high number means good quality or satisfactory, a "negative" where a low number or zero means a poor quality of life. Domain scores will be calculated and transformed into a scale ranging from zero to one hundred according to the algorithm.³⁶

3.8. Food consumption questionnaires

Two questionnaires will be applied to assess food consumption. A form of food consumption markers for individuals older than 5 years that is proposed by the Food and Nutrition Surveillance System. This tool aims to identify the frequency of pre-established food consumption in the last 7 days. The questionnaire has only ten items that are easy to understand

and apply. From item 1 to 5 are foods where daily consumption is recommended. Items 6 to 10 are foods that should be consumed eventually or should be avoided. The 24-hour Dietary Recall consists of a complete description of the interviewee's eating habits the day before the interview. The data to be obtained by the instrument is the type of food or preparation, quantity consumed, place and time of the meal. The participant will be asked to describe the part in homemade measures that will later be transformed into grams of the food. Nutritional information will be based on the Brazilian Food Composition Table.³⁷³⁸

3.9. 8-Stage Moriski Green - Adherence Questionnaire

To evaluate treatment adherence, the Eight-Item Morisky Therapeutic Adherence Scale was used, consisting of eight questions regarding the use of medication. The degree of therapeutic adherence will be determined according to the score resulting from the sum of the answers of the MMAS-8 questionnaire: high adherence (8 points), average adherence (6 or 7 points) and low adherence (<6 points).³⁹

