In relation to healthy lifestyle habits, adhering to a more restricted sodium diet is one of the most difficult to achieve, despite several efforts to reduce sodium intake in the population. Two-thirds of the salt consumption by the Brazilian population comes from the salt added directly to the meal. The numbers show that Brazilians consume more than twice – almost 12 grams (g) – of the amount recommended by the World Health Organization (WHO) [4]. Data from the Ministry of Health reveal that 90% of men and 70% of women consume more salt than the maximum recommended, 85.1% of adult Brazilians consider their salt consumption adequate [4]. Another important point between life habits is sedentary lifestyle, which can also contribute to the lack of adequate control of BP. There is much evidence that shows the benefit of physical activity to reduce BP, including providing the number of medications needed for control [3].

Therefore, it is essential to help patients adopt healthy measures to assist in the daily control of BP. As the barriers to therapeutic adherence are complex and varied, solutions to improve adherence at the population level should be multifactorial [14,15].

Several systematic reviews and meta-analyses have evaluated the impact of interventions on patients' adhering to antihypertensive medications and their benefits [16, 17].

Most interventions to improve the quality of AH care, medication and healthy habits and BP control are care based on a multidisciplinary team [18]. Different patient-centered models

with a multidisciplinary team showed an increase in the proportion of individuals with better blood pressure support and greater BP control [18,19,20,21,22].

One of the best and most effective models includes decision support systems (treatment algorithms), collaboration between team and patient, medication adherence, home BP monitoring, and patient self-care [23,24].

Recently, support systems such as electronic health records, remote monitoring based on new technologies and self-care support tools, can increase and intensify efforts based on the multidisciplinary team approach [25,26,27,28].

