In this sense, some studies are being conducted on the use of mobile technology to control hypertension, aiming at greater access to the patient, education and awareness of the disease, as well as the patient's engagement in their care [29,30,31,32,33]. In a previously developed study, it was seen that virtual distance or face-to-face teaching, through "e-learning", helps to reduce the effect of the white coat and the anxiety of hypertensive patients, with an improvement in adherence to treatment [34].

However, it is not yet known the best technological tools to help hypertensive patients to improve treatment adhering to healthy life habits and, and consequently avoid the complications of AH. In addition, this tool needs to be feasible to be used by patients or caregivers, regardless of social class, preserving their intimacy, privacy and still obtaining the desired health improvement results.

Based on these arguments, the hypothesis of the proposal is that the use of an application developed by artificial intelligence adapted to individual needs and customs can help improve therapeutic adherence and provide better BP control in patients with uncontrolled hypertension.

2. Primary objective

To evaluate the effectiveness of an artificial intelligence application developed for home monitoring compared to institutional standard follow-up in patients with uncontrolled hypertension in the following parameters:

- a) To obtain adequate control of blood pressure (< 140/90 mmHg) of the office and of the blood pressure ambulatory monitoring (< 135/85 mmHg at wakefulness)
- b) Improving adherence to drug treatment assessed by a validated questionnaire

- c) Reduce dietary sodium intake and 24-hour urinary sodium
- d) Increase the performance of physical activity evaluated by number of daily steps
- e) Reduction of body weight and abdominal circumference

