2.1. Secondary objective

- a) To evaluate the effects of the use of the monitoring application on: quality of life of patients with uncontrolled hypertension through WHOQOL questionnaire; sleep quality assessed by the Pittsburg questionnaire; anxiety level assessed by the HADS questionnaire; food consumption assessed by consumption questionnaires and food recall:
- b) Assess the ability of patients with uncontrolled hypertension to use the application

3. Methodology

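### Primary objective (c) gives dietary sodium intake no instrument, and the only candidate, the 24-hour recall, lists no item for added salt

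*Protocol*

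**What the plan says.** Item (c) of the primary objective (Protocol, section 2) reads "Reduce dietary sodium intake and 24-hour urinary sodium". It names two quantities. The second carries its own method. The first has none, whereas items (b) and (d) of the same list say how adherence and physical activity are assessed.

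Section 3.8 describes two food forms. The first has ten items: "This tool aims to identify the frequency of pre-established food consumption in the last 7 days". The second is the recall: "The 24-hour Dietary Recall consists of a complete description of the interviewee's eating habits the day before the interview". Its content is then listed: "The data to be obtained by the instrument is the type of food or preparation, quantity consumed, place and time of the meal". Portions are converted to grams, and "Nutritional information will be based on the Brazilian Food Composition Table". Section 3.8 does not mention sodium. Section 2.1(a) puts both forms under a secondary objective: "food consumption assessed by consumption questionnaires and food recall".

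The introduction states "Two-thirds of the salt consumption by the Brazilian population comes from the salt added directly to the meal", and gives the total: "The numbers show that Brazilians consume more than twice – almost 12 grams (g) – of the amount recommended".

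Section 3.1 has a 24-hour urine sample for sodium at the initial evaluation and repeats the laboratory tests at 12 months. Section 3.12 names 24-hour urine sodium among the quantitative variables to be compared, by a paired t-test. It names no dietary sodium variable.

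**The concern.** A component of the primary objective needs an identified measure, and its content has to be settled before data collection. An analysis plan cannot recover salt that no one asked about. Here the dietary component has no assigned measure, and the one form that could supply an amount has no stated place for what the protocol itself describes as the main source of salt. That source is also the one a patient controls most directly, so it is where an effect of the application would be expected.

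The recall is also self-reported by patients who know their arm, since only one arm receives a phone and the application. Under section 3.1 that arm gets automatic nutritional messages and a team contact every 4 weeks, while controls get reinforcement only at clinic visits. A recall-based sodium result could therefore miss a real change in added salt and also be tilted by reporting that differs between arms. If it disagreed with urinary sodium, section 2(c) would not say which of the two answers the objective.

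**Working it through.** There is no plan figure to reproduce. The check has two parts.

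**Which instrument could measure dietary sodium?**

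- Ten-item form: frequencies over 7 days, no quantities, so it yields no sodium amount.
- 24-hour recall: quantities and a food-composition table, so it could yield an amount. The fields listed are the food or dish, the quantity, the place and the time. Added salt is not among them.
- 24-hour urine: measures the second quantity in item (c) and does not depend on what the recall asks.

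So the recall is the only described candidate for the dietary component. The link is an inference, because the protocol does not state it.

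**How much could the recall miss?**

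Inputs from the introduction:
- total salt of almost 12 g, taken as 12 g a day (the text gives no time unit)
- share added at the meal, 2/3

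Assumption: *m* is the share of added salt that the recall does not record, the same at both time points. The protocol does not give it, so the full range 0 to 1 is shown.

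Added salt = 12 × 2/3 = 8 g. Other salt = 12 − 8 = 4 g.

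Share of total captured = 1 − *m* × 2/3.

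Take an illustrative 20% cut in added salt: 0.20 × 8 = 1.6 g, which is 1.6/12 = 13.3% of total salt, or 1.6/58.44 g/mol = 27.4 mmol of sodium. The recall shows (1 − *m*) × 1.6 g.

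| *m* | Salt captured | Share of total | 1.6 g cut shows as |
|---|---|---|---|
| 0 | 12 g | 100% | 1.6 g |
| 0.25 | 10 g | 83% | 1.2 g |
| 0.50 | 8 g | 67% | 0.8 g |
| 0.75 | 6 g | 50% | 0.4 g |
| 1 | 4 g | 33% | 0 g |

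The recall would miss more than half of total salt only if *m* × 2/3 > 1/2, that is, *m* > 0.75.

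**The case against.** The strongest reply is that the protocol never makes the recall a primary measure. Section 2.1 places it under food consumption, section 3.8 does not mention sodium, and section 3.12 names urinary sodium alone. On that view the sodium objective already rests on a laboratory measure. This stands, and it limits the point: a reader might infer that the primary sodium objective is measured by the recall, but no section says so.

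A reader might also infer that any cut in added salt would show as zero in the recall. The text does not support that either. Section 3.8 calls the recall a full account of the previous day and records preparation, so some salt may be captured. Whether the composition table's prepared dishes include salt cannot be told from the protocol. Zero is one end of the range.

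The two-thirds figure has limits too. It describes the general Brazilian population, not treated clinic patients, and it is unclear whether salt added directly to the meal includes salt used in cooking. Finally, reporting bias in patients who know their arm affects every questionnaire in this trial, not only this one.

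What the reply does not remove is the wording of section 2(c). It still lists dietary sodium intake as part of the primary objective. Either the recall is its measure, with no stated item for added salt, or the component has no measure at all.

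**Conclusion.** The point holds in limited form. Section 2(c) includes a dietary sodium component without an instrument, and the only described candidate has no stated provision for the source that the protocol's own introduction puts at two-thirds of intake. The possible loss runs from nothing to two-thirds of total salt, depending on an unrecorded share that the protocol does not give. The size also rests on reading 12 g as a daily figure and on applying a population figure to these patients.

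Urinary sodium protects the sodium objective as a whole, so this is not a fatal flaw. It is still worth correcting before data collection, because the gap concerns what is asked of patients and cannot be repaired at analysis.

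**What to change.** 1. In section 2(c), make 24-hour urinary sodium the sole measure of the sodium objective, compared between arms at 12 months with adjustment for the baseline value. Change section 3.12 to match: its paired t-test compares before with after, while section 2 asks for a comparison with standard follow-up.
2. Report any recall-derived sodium only under the secondary food-consumption objective in section 2.1(a), where the recall already sits.
3. In section 3.8, add one recall item on salt added at the table and in cooking, asked in both arms at the initial evaluation and at 12 months.

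One caveat on the baseline adjustment: as section 3.1 reads, the intervention arm's initial evaluation follows a 15-day adaptation period with the application, so its baseline urine may already reflect some use. The amended text should acknowledge this.

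The cost is a few sentences and one extra question. The urine collection is already planned. The downside is one fewer measure under the primary objective.

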3.10. Pittsburg Sleep Quality Questionnaire (PSQI)

The PSQI assesses the quality and sleep disorders during the period of one month, being a standardized questionnaire, simple and well accepted by patients. The instrument consists of 19 questions in self-report and five questions directed to the spouse or companion of room. The 19 questions are categorized into seven components, graduated in scores from zero (no difficulty) to three (severe difficulty). The components of the PSQI are: C1 subjective sleep quality, C2 sleep latency, C3 sleep duration, C4 habitual sleep efficiency, C5 sleep changes, C6 use of sleep medications and C7 sleep day time dysfunction. The sum of the values attributed to the seven components ranges from zero to twenty-one in the total score of the questionnaire indicating that the higher the number, the worse the sleep quality.⁴⁰

3.11. Anxiety Questionnaire - Hospital Anxiety and Depression Scale (HADS)

The HADS scale contains 14 multiple choice questions composed of two subscales, for anxiety and depression, with seven items each. The overall score on each subscale ranges from 0 to 21 and has been applied to patients in general without difficulty, with good clinical relationship.⁴¹

3.12. Statistical analysis

All analyses will be performed based on the complete population of the set of analyses, and all values of the clinic BP and the mean wakefulness of the ABPM will be included. The

characteristics of the patient at the initial visit will be described using mean \pm standard deviation or median deviation (quartiles) for continuous variables, or number (proportion in %) for categorical variables. To compare the main variables before and after using the application, the appropriate tests will be performed according to the type of the variable, that is, whether quantitative or qualitative. Thus, to compare the quantitative variables (blood pressure value, weight, body mass index, abdominal circumference, 24-hour urine sodium and questionnaire score), a comparative analysis of a paired t-test will be performed. For the nonparametric variables, the chi-square and kruskall wallis test will be used to compare them.

4. Expected results

The use of the artificial intelligence application for distance monitoring of patients with uncontrolled hypertension should provide greater engagement of patients and their families in treatment, and thus may lead to better blood pressure control, greater adhering to healthy lifestyle habits (decreased sodium intake, increased physical activity and improved quality of life) when compared to the follow-up currently performed at the institution. Better blood pressure control of these patients, who generally require a high number of medications, may consequently reduce the risks of complications and also the search for emergency services, which can harm the patient, and also encumber the health service. In addition, the integrated participation of a multidisciplinary team more actively ensures greater involvement with patient care, without the need for frequent returns to the Unit for better blood pressure control.

5. Timeline

Month	Activity
1st to 2nd month	Selection of participants
2nd to 3rd month	Signature of the GDPL and training of patients with application
5th to 6th month	Consultation for data collection and delivery of the blood pressure measurement device
7th to 12th month	Monitoring patients by staff through the application
7th to 12th month	Consultation for data collection and delivery of the blood pressure measurement device

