The control group (N= 50) will perform the same initial evaluation and answer the same questionnaires as described above for the intervention group. In this evaluation will receive guidance regarding the adoption of life habits by the multidisciplinary team. The control group will receive reinforcement of guidance only in clinic face-to-face visits.

The visits of the study after the patient's inclusion will take place every 12 weeks (Visits 2, 3, 4 and 5), totaling 4 visits after the initial visit, with the final visit after 12 months. Patients will perform 24-hour ambulatory blood pressure monitoring (ABPM) at visits 2, 3 and 5. In visits 2 to 5, the patient will have the measurement of blood pressure from the office, weight and abdominal circumference, and data on symptoms and events that occurred (hospitalizations, emergency room visits, symptoms) will be collected. In the last visit (12-month), in addition to these measures, the questionnaires performed on the first visit and laboratory dosages will be repeated.

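### Section 3.12 says all clinic and awake ambulatory BP values will be included but assigns BP to a two-value before/after paired t-test, without saying how four clinic and three ABPM follow-up values enter it

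*Protocol*

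**What the plan says.** Section 3.12 opens with a sentence that fixes both the data to be used and the analysis population. On the data, it promises that "all values of the clinic BP and the mean wakefulness of the ABPM will be included". On who is analysed, its rule is a full analysis set: "All analyses will be performed based on the complete population of the set of analyses". The section then sets the comparison ("To compare the main variables before and after using the application") and, for quantitative variables including the blood pressure value, the test: "a comparative analysis of a paired t-test will be performed". Two further tests are named, but not for BP as a quantitative value: "For the nonparametric variables, the chi-square and kruskall wallis test will be used to compare them".

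The visit schedule is in section 3.1: "totaling 4 visits after the initial visit, with the final visit after 12 months". For clinic BP, "In visits 2 to 5, the patient will have the measurement of blood pressure from the office, weight and abdominal circumference". For ambulatory BP, "Patients will perform 24-hour ambulatory blood pressure monitoring (ABPM) at visits 2, 3 and 5".

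The primary objective (section 2) is a comparison of the application with the institution's standard follow-up. Its BP component is control below clinic and awake-ABPM thresholds.

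**The concern.** A paired t-test uses one before and one after value per patient. The schedule yields four candidate after values for clinic BP and three for awake ABPM. The protocol names neither the visit that counts as after nor a rule for reducing several values to one. The inclusion rule and the test therefore do not fit together without a step that is not written down.

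Two things are at stake. First, the routes that could fill the gap range from a test at its nominal level to one with about four times that false-positive rate, and the choice could be made after results are seen. Second, all of them are within-patient tests, so none delivers the between-arm comparison that section 2 asks for.

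**Working it through.** **Inputs from the protocol.** 100 patients, 50 per arm (section 3.1). Clinic BP at the initial evaluation and visits 2, 3, 4 and 5, so k = 4 follow-up values. Awake ABPM as an eligibility value and at visits 2, 3 and 5, so k = 3. The three clinic readings within a visit are averaged (section 3.2), so the repeats counted here are across visits.

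**Assumptions.** The protocol gives no alpha, SD, correlation or dropout rate, and there is no stated figure to reproduce. I take two-sided alpha 0.05 and equal correlation ρ between any two visits. Simulations used 20,000 runs, 50 patients, no true change, and ρ = 0.3, 0.5 and 0.7.

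**Route 1: baseline against visit 5.**
- Clinic: 3 of 4 follow-up values unused (75%), or 300 of 400 planned across 100 patients.
- ABPM: 2 of 3 unused (67%), or 200 of 300.
- If nothing is imputed, patients without visit 5 also leave the test. An assumed 5% to 30% without a final value means 5 to 30 of the 100.

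**Route 2: one paired test per visit.** If the tests were independent, the chance of at least one false positive would be 1 − 0.95^k, which is 0.185 for k = 4 and 0.143 for k = 3. Tests sharing a baseline are correlated, so the true value is lower: simulated 0.154 to 0.157 (clinic) and 0.123 to 0.124 (ABPM).

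**Route 3: every follow-up/baseline pair pooled as independent.** With unit variance, each change has variance 2(1 − ρ). Two changes sharing one baseline have covariance ρ − ρ − ρ + 1 = 1 − ρ, so they correlate 0.5 whatever ρ is. The variance is understated by the factor 1 + (k − 1) × 0.5, and the true level is 2 × [1 − Φ(1.96 / √factor)].
- Clinic: factor 2.5, 1.96/1.581 = 1.240, level 0.215 (simulated 0.212 to 0.218).
- ABPM: factor 2.0, 1.96/1.414 = 1.386, level 0.166 (simulated 0.163 to 0.169).
- Sensitivity: if baseline correlates 0.5 with follow-up and follow-ups correlate 0.7 with each other, the changes correlate (0.7 − 0.5 − 0.5 + 1)/1 = 0.7. The clinic factor is then 3.1 and the level about 0.27.

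**Route 4: per-patient mean of follow-up values against baseline.** The level stays near 0.05 (simulated 0.047 to 0.050). The variance of the change is (1 + 1/k)/2 of that in route 1: 0.625 (clinic) and 0.667 (ABPM). It estimates average BP over the year, not BP at 12 months.

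| Route | Uses all values | False-positive chance, clinic / ABPM | Month-12 result | Compares arms |
|---|---|---|---|---|
| 1. Visit 5 only | no | 0.05 / 0.05 | yes | no |
| 2. Test per visit | yes | about 0.15 / 0.12 (any visit) | one of several | no |
| 3. Pooled pairs | yes | about 0.22 / 0.17 | no | no |
| 4. Follow-up mean | yes | about 0.05 / 0.05 | no | no |

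**The case against.** The best reply is that the all-values clause sits in the sentence on the analysis population and may only mean that no reading is excluded. On that view, which visit counts as after is a detail for a statistical analysis plan. This partly stands: had the protocol left the method open, the point would be a request for clarification. But the protocol names the test. A later plan that follows it would still hold a within-patient test for a between-arm objective, with most of the scheduled follow-up BP values either unused or brought in by an unstated rule.

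A reader might infer several stronger things that the documents do not support:
- **That the plan pools readings as independent pairs.** Section 3.12 never says so. The 0.22 and 0.17 describe one possible reading, under equal correlation.
- **That the plan must either pool or discard.** Routes 2 and 4 use every value without pooling, and both can keep patients who lack visit 5.
- **That the analysis is restricted to completers.** This needs visit 5 to be the after value and no imputation; the protocol states neither. It gives no dropout rate, so any bias figure would be an assumed scenario, and none is claimed here.
- **That the paired t-test is the only test in the section.** Chi-square and Kruskal-Wallis are also named. Neither is assigned to BP as a quantitative value, and neither handles repeated values within a patient.
- **That the contradiction extends to weight and waist.** The all-values clause covers only clinic BP and awake ABPM.

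**Conclusion.** The point holds as a mismatch within the protocol. The inclusion rule for clinic BP and awake ABPM cannot be carried out with the named test unless a step is added, and the protocol does not give that step. The counts (four and three follow-up values; 75% and 67% unused if only visit 5 is taken) come directly from the schedule. The error rates, from about 0.05 up to about 0.22 for clinic BP and 0.17 for ABPM, rest on an assumed two-sided 0.05 and equal correlation between visits; under the alternative correlations shown, the pooled clinic figure is about 0.27. They show how far the choice of route matters and do not predict what the trial will do. Whichever route is taken, the test does not compare the application with standard follow-up. That makes this more than missing detail, because the named test is the wrong one for the objective and for the data collected.

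**What to change.** In section 3.12, replace the paired t-test for clinic BP and awake ABPM with a repeated-measures mixed model. Analyse all randomised patients in their assigned arm, whether or not they kept using the application. Include the baseline value, visit, arm, arm-by-visit and a within-patient covariance, and take the month-12 between-arm contrast as the result. Every scheduled follow-up value then enters, and a patient with any follow-up value contributes.

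Weight and waist are also measured at visits 2 to 5 and would benefit from the same model. That is an improvement and is not needed to resolve the contradiction.

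The yes/no BP-control objective in section 2 is not covered by this change and needs its own between-arm analysis.

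The cost is about two sentences and slightly more analysis work, with no new data. The model assumes that values are missing at random given the observed ones, which should be stated. A patient with no follow-up value at all still adds nothing to the contrast.
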